12.2	Statistical Analysis	55
13.	REGULATORY	58
14.	REFERENCE LIST	59

List of abbreviations

AE	Adverse Event
AI	Aromatase Inhibitor
ALT	alanine aminotransferase
AST	aspartate aminotransferase
b.i.d.	bis in diem/twice a day
BMD	Bone mineral density
CEE	Conjugated equine estrogen
CI	Confidence interval
CRF	Case Report/Record Form
CS&E	Clinical Safety and Epidemiology
CR	Clinical Research
CRO	Contract Research Organization
DCIS	Ductal carcinoma in situ
ECG	Electrocardiogram
ER	Estrogen receptor
HR	Hazard ratio
IEC	Independent Ethics Committee
i.v.	intravenous(ly)
IRB	Institutional Review Board
MPA	Medroxyprogesterone acetate
o.d.	omnia die/once a day
p.o.	per os/by mouth/orally
REB	Research Ethics Board
RPFNA	Random periareolar fine needle aspiration
SAE	Serious Adverse Event
SHBG	Sex hormone binding globulin
SOP	Standard Operating Procedure
WHI	Women's Health Initiative
WHO	World Health Organization

SCHEMA

Prevention Visit

Risk assessment of postmenopausal potential study subjects currently using hormones to control menopause symptoms.

Gail 5-year risk $\geq 1.7\%$ and/or a relative risk of $\geq 3X$ that for the average woman of the same age, as calculated by the NCI Breast Cancer Risk Assessment Tool; or a 10-year relative risk of $\geq 3X$ that for the population, as calculated by the IBIS Breast Cancer Risk Evaluation Tool; or BRCA1/2 mutation carrier; or prior ADH, DCIS, LCIS,

Qualifying RPFNA visit

Bone densitometry (DEXA) within two years prior to study entry

No change in dose or route of hormones for six months

Normal mammogram within three months of RPFNA.

Biomarker Qualifiers for Trial Participation

RPFNA = Epithelial hyperplasia +/- atypia with Ki-67 $\geq 1.5\%$

RNA Extraction plus storage for later qRTPCR; History, breast and physical exam

Study Entry Visit (within three months of RPFNA)

CBC chem. profile, fasting lipid profile, C-reactive protein,

bioavailable testosterone and estradiol,

serum bone turnover markers (osteocalcin and N-telopeptide),

25-OH Vitamin D levels; Mammogram digitized for density measurement

Complete hot flash scores, brief fatigue inventory, BCPT Symptom Checklist and HAQ Fibromyalgia Questionnaire; History, breast and physical exam (if not previously done)

Randomization to letrozole 2.5 mg/day or placebo; while continuing same dose of hormone replacement

monthly phone contacts

Six Month Study Visit

CBC chem. panel, fasting lipid profile, CRP, bioavailable estradiol and testosterone,

osteocalcin and N-telopeptide, 25-OH Vitamin D levels, reserve serum for letrozole levels

Mammogram, density measurement

Repeat questionnaires, history and physical,

RPFNA and associated biomarkers; DEXA scan if not continuing on open label

Optional Open Label Letrozole 2.5 mg/d

monthly phone contacts

12 Month Study Visit (for women choosing open label letrozole)

Repeat assessments performed at six month visit; DEXA scan at completion

Goal: 96 evaluable subjects at six month visit

1.0 Objectives

Our primary hypothesis is that proliferation and expression of other estrogen response genes in hyperplastic breast tissue obtained by RPFNA from high risk women on chronic HRT will be favorably modulated by six months of letrozole relative to placebo without substantially increasing hot flashes or worsening overall quality of life.

To test our hypothesis, we have formulated the following objectives:

- 1.1 To determine whether Ki-67 in hyperplastic foci of breast epithelium obtained by random periareolar fine needle aspiration from postmenopausal high-risk women on HRT is reduced by six months of letrozole.
- 1.2 To determine if letrozole causes an increase in hot flashes, fatigue, pain, stiffness; a deterioration in overall quality of life; as well as deleterious changes in bone turnover markers, total cholesterol:HDL ratio, and C-reactive protein.
- 1.3 To determine if morphologic characteristics as assessed by nuclear morphometric measurements and semiquantitative Masood index score improve with six months of letrozole.
- 1.4 To determine if six months of letrozole in women on a stable dose of hormone replacement results in consistent down modulation of estrogen responsive genes, particularly pS2 and GREB-1.

At the conclusion of this proof of principle study, we will have established a firm clinical and biological basis for a large randomized study of letrozole versus placebo in high-risk postmenopausal women requiring hormone replacement for symptom control with development of breast cancer as an endpoint. If aromatase inhibitor treatment is found to reduce risk of breast cancer in women receiving hormone replacement, it would provide middle age women with tools to alleviate perimenopausal symptoms while minimizing breast cancer risk.

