3.0 Summary of Study Plan

This is a multi-institution double-blind placebo-controlled trial to whose main endpoint is to determine if 6 months of letrozole (2.5 mg daily) can reduce proliferation as assessed by Ki-67 in high risk postmenopausal women on systemic hormone replacement therapy who have RPFNA evidence of hyperplasia with atypia or borderline atypia, and a minimum Ki-67 in a hyperplastic foci of $\geq 1.5\%$. Secondary efficacy endpoints include assessment of change in morphology by nuclear morphometry and the semi-quantitative Masood score index and change in qRT-PCR assessed estrogen response genes (GREB-1, pS2). Mammographic density and bioavailable estradiol and testosterone will be assessed as well. No difference in change between letrozole versus placebo is expected for mammographic breast density, Masood Index score, or serum hormones, but significant reductions are expected in Ki-67, expression of estrogen response genes by qRT-PCR, and the proportion of cells deemed abnormal by nuclear morphometry. Other secondary endpoints include change in biomarkers associated with bone and cardiovascular health, toxicity measurements using the NCI CTCAE version 3.0, BCPT Symptom Check List (Mayo Clinic) hot flash score, general fatigue inventory the Fibromyalgia Impact Questionnaire from the Health Assessment Questionnaire, (which assessed joint stiffness and functional impact). These are validated questionnaires and it should take no more than 10-15 minutes to complete all three questionnaires. We predict there will be little difference in most parameters between placebo and letrozole at 6 months in these women continuing their HRT. Exceptions may be arthralgias, fatigue in a minority of women, particularly those with sub-optimal 25-OH vitamin D levels. We will be assessing baseline and six month 25-OH vitamin D levels to determine if women with an increase in bone turnover markers, fatigue and arthralgias are likely to have underlying vitamin D insufficiency which is unmasked by use of letrozole. Subsequent to the 6-month RPFNA for assessment of biomarkers, toxicity and quality of life assessments, all women may receive optional open-label letrozole for an additional 6 months, followed by a third RPFNA and biomarker assessment. The primary purpose of the subsequent 6 months open label letrozole is to facilitate recruitment, but also to assess biomarker and toxicity endpoint changes with longer treatment. A DEXA scan will be performed at completion of study to document any effects on bone health.

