10.7 Quality of Life Evaluations

The most frequent adverse events in our pilot trial were arthralgias, fatigue and hot flashes. Consequently, in addition to utilizing the Breast Cancer Prevention Trial (BCPT) symptom scale (used as part of NSABP prevention trials) [Ganz 1995; Day 1999], we will use specific tools geared to the most prevalent symptoms in the pilot study.

The BCPT symptom checklist is a 42 item list of problems common to peri and postmenopausal women and those undergoing anti-hormonal

treatment in prevention trials. Women are asked if they have had the symptom in the past four weeks. If they answer yes, they are asked to grade the severity (0-4). This tool can be used to compute a total score or individual or related items of interest (e.g., three items relate to joint stiffness and arthralgias) may be scored [Stanton 2005].

The Mayo Clinic Hot Flash scoring system was developed by Loprinzi et al. Subjects are asked about their daily number of hot flashes and rate usual severity from 1 to 4. The frequency is multiplied by usual severity to obtain a total score [Loprinzi 2002].

We do not expect an increase in symptoms or hot flash scores for women randomized to letrozole.

The Fibromyalgia Impact Questionnaire (HAQ) is a validated tool routinely used by rheumatologists to evaluate pain, stiffness, and physical functioning. Individual domains or a total score can be utilized in assessment [Wolfe 2004].

The brief fatigue inventory asks the woman to rate her current as well as worst and usual fatigue in the past 24 hours. It also asks her to rate how the fatigue has affected mood, general activity, walking, work relations, and enjoyment of life [Mendoza 1999].

We do not expect an increase in joint pain, stiffness or fatigue for women randomized to letrozole, unless a woman has suboptimal levels of 25-OH vitamin D.

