12.1 Sample Size and Power

The primary outcome of interest is efficacy of letrozole relative to the placebo, thus the pre- to post-treatment change in a proliferation index (percent of cells expressing Ki-67) is the basis of the power analyses. From our pilot study, the average percentage of cells expressing Ki-67 at baseline was 6.4%, and the average change in percent of cells expressing Ki-67 was a 3.7% reduction, for subjects meeting the same eligibility requirements as will be used in this proposed trial.

A 1:1 randomization of 96 evaluable subjects will provide 90% power to detect an effect size of 0.67 standard deviations with a Type I error rate of 5% using a two-sample, two-sided t-test. In other words, if one assumes a common standard deviation of change of 5.5% (as observed in the pilot study for the 33 subjects matching eligibility criteria for the proposed trial) for both placebo and letrozole groups and if mean change for placebo is zero, then there will be 90% power to detect an average change of 3.7% in Ki-67 in the letrozole group with a Type 1 error rate of 5%. Note that the 3.7% reduction is what was seen in the pilot study. Using a conservative drop-out rate of 10% (it was 2% in the pilot study), enrollment of 108 subjects should provide the required 96 evaluable subjects for the primary endpoint.

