Evaluation of drug-induced hormonal changes - We will examine whether Letrozole has any effects on serum levels of bioavailable estradiol, and testosterone, determined at baseline and after six months of study medication. We will determine whether addition of letrozole alters the frequency of menopausal symptoms.

Adverse Events and Quality of Life – Change from baseline to six months for hot flash score (Mayo Clinic), fatigue (brief fatigue inventory), overall quality of life (BCPCT), bone turnover markers, HDL/total cholesterol, and C-reactive protein will be compared between the two groups using the two-sample t-test. Similarly, demographic variables (e.g., age, education) and hormonal levels will be tested for use as covariates on each of these endpoints. We will also assess the effects of change in serum hormones (if any) and baseline 25-OH vitamin D levels on incidence and severity of arthralgias and fatigue.

Within Letrozole Comparisons at baseline, 6 and 12 months - On all of our quantitative continuous measures we will perform a repeated measures analysis comparing the 6 and 12 month values to baseline and also with each other. This will give us some preliminary indication whether there is any benefit or detriment of 12 months of treatment. For all the above analyses of exploratory endpoints, as well as for changes in proliferation, results from the 12-month timepoint (following six months of open-label treatment with active agent) will also be analyzed and compared to the baseline and six month values with caution since the double-blind, randomized nature of the comparison is no longer present. However, since

every effort is made to conduct the assessment and quantification of biomarkers without knowledge of treatment arm, the results could be informative.

Since this is a phase IIB trial, the power and sample size for the primary endpoint was determined with a two-sided type I error rate of 5%. All subsequent secondary, tertiary and exploratory analyses will also be tested with a two-sided type I error rate of 5%. This may result in an elevated false positive rate for these secondary and tertiary analyses, however, since this is a Phase IIB study, we felt to control the type I error rate for the secondary, tertiary and exploratory analyses would be too conservative.

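### The hypothesis says letrozole will not substantially increase hot flashes or worsen quality of life, but the plan's difference t-test has no margin or confidence-interval rule by which that could be concluded

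*Combined protocol and SAP*

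**What the plan says.** The primary hypothesis in section 1.0 joins a biomarker effect to a tolerability condition: the effect is to come "without substantially increasing hot flashes or worsening overall quality of life". No section puts a number on what counts as substantial. Objective 1.2, which serves this part, is "To determine if letrozole causes an increase in hot flashes, fatigue, pain, stiffness; a deterioration in overall quality of life".

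Section 12.2 (Adverse Events and Quality of Life) names the endpoints, "Change from baseline to six months for hot flash score (Mayo Clinic), fatigue (brief fatigue inventory), overall quality of life (BCPCT"), and says that they "will be compared between the two groups using the two-sample t-test". I read BCPCT there as the BCPT symptom checklist of section 10.7. Section 12.2 puts all secondary analyses at a two-sided 5% level without multiplicity control. Section 12.1 bases the sample size on change in Ki-67 alone.

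The expected result is a null. Section 3.0 says "We predict there will be little difference in most parameters between placebo and letrozole at 6 months", with arthralgia and fatigue in a minority as possible exceptions. Section 10.7 says "We do not expect an increase in symptoms or hot flash scores for women randomized to letrozole".

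**The concern.** A difference test can reject equality. Failing to reject does not show that an increase is small. The hypothesis makes a claim of that second kind, and the plan pairs it with a test of the first kind. No margin, confidence-interval rule or power statement links them.

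The risk is that a p-value above 0.05, which is the result the plan predicts, is reported as confirming the tolerability condition. The background section already sums up the single-arm pilot in such terms: section 2.2, item 6 offers the lack of a significant change in serum estradiol as part of the rationale.

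The point matters in this population. Section 2.1 names side effects and quality of life as major reasons why women decline anti-estrogen prevention. Sections 2.2.4.1 and 6.7.1 report more hot flashes on letrozole than on placebo in the extended adjuvant setting (net difference 4%). Section 1.0 intends the results to ground a large randomised trial.

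**Working it through.** **1. The plan's own figure.** Section 12.1 gives a difference of 3.7 and an SD of 5.5 percentage points, two-sided 5%, 90% power.
- Effect size: 3.7 / 5.5 = 0.673.
- Per arm: 2 × (1.960 + 1.282)² / 0.673² = 46.4, so 47. The plan uses 48.
- Noncentral-t power at 48 per arm: 90.4% (90.1% at 0.67).
- Enrolment: 96 / 0.9 = 106.7, so 107. The plan says 108.

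The Ki-67 sample size reproduces.

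**2. Inputs for the tolerability scores.** 48 per arm (96 / 2) and two-sided 5% come from sections 12.1 and 12.2. The documents give no SD for change in the hot flash or BCPT score and no margin. The effect sizes below are therefore assumptions, in units of the SD of change.

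**3. Power of the planned t-test.** Degrees of freedom 94, critical value 1.9855, noncentrality d × √(48/2) = 4.899d.

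| True worsening | Power | Non-significant |
|---|---|---|
| 0.3 SD | 30.7% | 69% |
| 0.4 SD | 49.2% | 51% |
| 0.5 SD | 67.9% | 32% |

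If all 108 women contribute (54 per arm), power at 0.4 SD is 54.0%, so 46% of trials are still non-significant.

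**4. What a non-significant result leaves open.** The 95% CI half-width is 1.9855 × √(2/48) = 0.405 SD. If the observed increase falls just short of significance, at about 0.405 SD, the upper limit is 2 × 0.405 = 0.81 SD.

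**5. What the sample size could support with a margin.** For one-sided 2.5%, true difference 0 and normal approximation, the smallest supportable margin at 48 per arm is
- 80% power: (1.960 + 0.842) × √(2/48) = 0.57 SD;
- 90% power: (1.960 + 1.282) × √(2/48) = 0.66 SD.

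Power at 48 per arm for margins of 0.2, 0.3, 0.4, 0.5, 0.6 and 0.67 SD is 16%, 31%, 50%, 69%, 84% and 91%.

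**6. A rough translation into hot flash points.** Section 2.8 reports for 42 pilot women a median change of 0 (-8 to +9), with 17% up, 14% down and 69% unchanged, which is 7, 6 and 29 women. I take -8 to +9 as the range and assume whole-number changes.
- Smallest SD (one +9, six +1, one -8, five -1, 29 zeros): sum 2, sum of squares 156, SD = √((156 − 2²/42)/41) = 1.95.
- Largest SD (seven +9, six -8, 29 zeros): sum 15, sum of squares 951, SD = √((951 − 15²/42)/41) = 4.80.

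The CI half-width is then 0.8 to 1.9 points. The number per arm for 80% power to exclude a margin is 60 to 363 for 1 point, 15 to 91 for 2 points and 7 to 41 for 3 points. Whether 48 per arm is enough depends on a margin and an SD that the documents do not state.

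**The case against.** Several points on the other side have force.

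- **No misreading is planned.** A reader might infer that the plan treats p > 0.05 as proof of no harm. No section says so. The statements in sections 3.0 and 10.7 are expectations, not decision rules, and objective 1.2 is worded as a search for harm, which a two-sided difference test fits. This stands: the misreading is a risk, not a stated intention. But the hypothesis that the objective serves claims absence of a substantial increase, and no rule is given for reaching that conclusion.
- **The sample size is not shown to be inadequate.** A reader might also infer that 96 women cannot support the claim. Steps 5 and 6 do not bear that out: a wide enough margin is within reach. What is missing is the margin and the way of reading the result.
- **These are secondary endpoints.** Section 3.0 lists them so, the primary outcome is Ki-67, and the follow-on trial would again be placebo-controlled and could measure symptoms again. This lowers the stakes. It does not make a non-significant result evidence of no increase.
- **The t-test is not the only tolerability analysis.** Section 12.2 also plans Fisher's exact test on grade 3 toxicity or early discontinuation, covariates for these endpoints, a look at the frequency of menopausal symptoms, and repeated measures to 12 months. The Fisher test does not use these scores, the repeated measures compare time points within letrozole, and the symptom-frequency item names no method. None brings a margin.
- **No multiplicity control.** For detecting harm, this favours finding a worsening. That is true, but it does not help to exclude one.

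**Conclusion.** The concern holds in this form: the plan as written has no valid route to the tolerability part of its primary hypothesis. The only between-arm comparison specified for the hot flash and BCPT scores is a difference test without margin, interval criterion or power, and a non-significant result from it would not support the claim.

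On assumed SD units and 48 per arm, worsening of 0.3 to 0.5 SD would be non-significant in about 69% to 32% of trials, and a just non-significant increase would be compatible with worsening of about 0.8 SD. The documents do not say that effects of this size are substantial. Nor do they show that the claim is out of reach: a margin of about 0.57 SD or wider would have 80% power if the true difference is zero.

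Confidence is high that the rule is missing. How the sponsor would read a null result is inference.

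**What to change.** In section 12.2, for the hot flash score and the BCPT total score:

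1. Report the letrozole-minus-placebo difference in six-month change with its two-sided 95% confidence interval.
2. Allow the conclusion of no substantial increase or worsening only if the interval excludes worsening beyond a margin that the sponsor states, with its justification, before unblinding. Give the power for that margin at the planned sample size.
3. If no margin is set, state that a non-significant t-test will not be reported as evidence of no increase, and treat this part of the hypothesis as descriptive.

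The change is to SAP wording only and needs no further women or data. The price is that a favourable tolerability claim becomes harder to make, and under item 2 a margin has to be written down and defended.

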2.0 Background

2.1 Need For Development of Prevention Intervention for Postmenopausal women on HRT for Control of Menopausal Symptoms

It is estimated that one quarter of postmenopausal women in the United States take hormone replacement therapy [National Institutes of Health 2005]. This is primarily because nothing else is as efficient in relieving perimenopausal symptoms [Barton 2002; Nelson 2004]. There is no identified primary prevention strategy for those women who are both at high risk for breast cancer because of family history or prior pre-cancerous biopsy and who need hormone replacement therapy to alleviate perimenopausal symptoms [Fabian 2005C; Wickerham 2006]. Standard drug prevention therapy for postmenopausal women is tamoxifen or raloxifene and major prevention Phase II clinical trials in postmenopausal women are investigating use of aromatase inhibitors [Cuzick 2005]. Current expert opinion and ASCO guidelines suggest that hormone replacement not be used with tamoxifen [Vogel 2001; Chlebowski 2002] and clinical trials with aromatase inhibitors (AIs) or raloxifene exclude women who use hormone replacement therapy. Concerns about side effects and quality of life are major reasons why the majority of women have avoided primary prevention therapy with anti-estrogenic drugs in the past [Port 2001; Vogel 2002; Tchou 2004; Bober 2004]. Advice to a symptomatic high risk woman that she discontinue hormones in order to take anti-estrogens has a poor likelihood of being heeded as this would force her to both give up an effective therapy for her menopausal symptoms in addition to starting a medication which has a substantial chance of worsening them. An effective prevention strategy which would permit symptomatic high risk women to continue taking hormone replacement is needed and is the subject of this protocol.

2.2 Rationale for Use of Aromatase Inhibitors in High Risk Post-Menopausal Women Taking Hormone Replacement Therapy

The rationale for use of aromatase inhibitors as primary prevention therapy in high risk women taking hormone replacement comes from six lines of evidence.

1. Up-regulation of aromatase in areas of benign breast disease which is common in high risk women.
2. Breast aromatase activity is responsible for the majority of breast tissue estrogen in postmenopausal.
3. Aromatase inhibitors have been shown to be more effective than tamoxifen in adjuvant trials in preventing contra-lateral cancers in postmenopausal women.
4. Pre-clinical data in aromatase over-expressing animals suggests the aromatase inhibitor, letrozole, is effective in a high estrogen environment.

5. Low dose estradiol may prevent some side effects associated with aromatase inhibitors.

6. Our pilot study of 6 months of letrozole in high risk postmenopausal women on a stable dose of hormones showed a substantial reduction in proliferation in hyperplastic epithelium obtained by random periareolar fine needle aspiration without a significant change in serum estradiol or increase in perimenopausal symptoms.

These lines of evidence are explored in more detail below.

